13.1.3 Efficacy Analysis

Two-sided tests at a significance level of $\alpha=5\%$ will be used throughout unless otherwise stated. The null hypothesis is that lubiprostone is equal to placebo against the alternative that lubiprostone is different to placebo. All analyses will be performed using the FAS. Analyses specified for the PP are to be regarded as supportive evidence. There will be no adjustment for multiplicity.

All efficacy endpoints will be summarized by treatment and visit. If Baseline measures are also defined and collected for an efficacy endpoint then change from baseline at each visit will also be presented by summary statistics by treatment and visit. Baseline is defined as the last recorded measurement prior to treatment. For parameters based on diary data, Baseline values will be derived using the data from the Screening Period.

Centers may be pooled geographically if necessary for analysis purposes.

The last observation carried forward (LOCF) technique will be used to impute missing values. For a given subject, the most recent nonmissing treatment-period data point will be carried forward to the subsequent week where data are missing. Supportive analyses will be conducted without missing value imputation (ie, without LOCF) and with a ‘worse-case’ scenario where missing values are assigned the worst case values recorded in the study by any subject for that endpoint at that time.

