Additionally the endpoint will be analyzed using robust analysis of variance (ANOVA) models with center and treatment in the model as a sensitivity analysis.

If there are no SBMs during the week or if there are SBMs but all ratings are missing, then the LOCF method will impute the average from the average used for the most recent week. For Week 1 analysis where there is no value to carry forward then a value of 4 will be assumed. This assumption will be carried into later weeks if LOCF does not provide an estimate.

Mean Degree of Stool Consistency (Week 1, 2, 3, and 4)

For each BM patients should indicate the type of stool consistency associated with that BM. The degree of stool consistency is assessed using the Bristol Stool Scale [3]; a 7 point scale, where decreasing values indicate harder stools:

Type 1		Separate hard lumps, like nuts (hard to pass)
Type 2		Sausage-shaped but lumpy
Type 3		Like a sausage but with cracks on its surface
Type 4		Like a sausage or snake, smooth and soft
Type 5		Soft blobs with clear-cut edges (passed easily)
Type 6		Fluffy pieces with ragged edges, a mushy stool
Type 7		Watery, no solid pieces, entirely liquid

Stool consistency will be analyzed in the same manner described for the degree of straining. For Week 1 analysis, where there is no value to carry forward, then a value of 1 will be assumed. This assumption will be carried into later weeks if LOCF does not provide an estimate.

CROSS-REGIONAL TEMPLATE

Template Number: C-TMPL-DO-801 **Page:** 21 of 28
Version Number: 1.2 **Effective Date:** 14 Sep 2015
This version replaces: 1.1
Parent Document: C-SOP-DO-800
Template Title: Statistical Analysis Plan (Legacy Takeda)

Weekly Abdominal Symptoms Score (Bloating and Discomfort) (Week 1, 2, 3, and 4)

The abdominal symptom score should be completed by patients in their diary, every 7 days on the last day of each treatment week upon waking in the morning. Patients should indicate the degree of abdominal bloating and discomfort experienced over the past week.

Abdominal Bloating	0 = None: No abdominal distension 1 = Mild: Slight abdominal distension 2 = Moderate: Abdominal distension clearly felt 3 = Severe: Severe abdominal distension 4 = Very severe: Extremely strong abdominal distension

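### SAP 7.8.2 scores a Week 1 with no SBM as worst straining or hardest stool in the main analysis, and the SAP omits the protocol's analysis without imputation that would show its influence

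*SAP*

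**What the plan says.** SAP 7.8.2 averages straining over the SBMs of a week and compares arms by a van Elteren test stratified by center, on the FAS. Imputation is triggered "If there are no SBMs during the week or if there are SBMs but all ratings are missing", and "then the LOCF method will impute the average from the average used for the most recent week". The straining text then reads "For Week 1 analysis where there is no value to carry forward then a value of 4 will be assumed"; 4 is the top of its 0 to 4 scale. Stool consistency follows the same scheme, except that "then a value of 1 will be assumed", the hardest type on the 1 to 7 scale. Both scores pass into later weeks when carry-forward gives nothing else. The only sensitivity analysis listed for these endpoints is "robust analysis of variance (ANOVA) models with center and treatment in the model as a sensitivity analysis", with no different missing-data rule.

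Protocol 13.1.3, in its general efficacy text, says: "Supportive analyses will be conducted without missing value imputation (ie, without LOCF"). In the same sentence it adds, also as supportive, a worst-case analysis in which "missing values are assigned the worst case values recorded in the study by any subject for that endpoint at that time". Its carry-forward rule is limited to on-treatment data: "the most recent nonmissing treatment-period data point will be carried forward".

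SAP 7.8.1 and 7.8.2 keep the worst-case analysis for SBM frequency. No analysis without imputation appears in SAP 7.8 to 7.8.3 for any endpoint. SAP 7.13 says the SAP adds detail and further analyses; it reports nothing as dropped.

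**The concern.** Having no SBM in a week is a frequency outcome, and frequency is the primary endpoint, where a drug effect is expected. If such weeks are more common on placebo, scoring them 4 or 1 moves the placebo arm to the bad end of scales meant to describe the stools that were passed. A pure frequency effect can then be reported as less straining and softer stools. Protocol 6.2 presents these endpoints as adding to frequency, so the reader needs to tell the two effects apart.

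No other planned test does this:

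- The robust ANOVA uses the same filled values.
- The extra analysis of subjects with under 4 diary days (SAP 7.8) covers only the primary endpoint and still fills with baseline.
- The per-protocol set is not used for secondary endpoints.

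A smaller wording point goes with this. SAP 7.8 has a general rule that baseline replaces absent post-baseline data, and says details for each parameter follow. The natural reading is that 7.8.2 governs and screening values are not carried into Week 1. The SAP does not say so, and it leaves out the protocol's restriction to treatment-period data.

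Bloating and discomfort get 4 only when ratings are missing, so this mechanism does not apply to them.

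**Working it through.** **Inputs from the documents.** Week 1 SBM mean and SD per arm are in protocol Table 4.a. The design values are means 4 and 5.9 with SD 4, and 102 per arm (SAP 6.0 and 4.2). The protocol summary gives about 10 sites. SAP 6.0 names SC0232 as the source of the means, and its 3.99 and 5.89 match them (protocol 13.3 names SC0131).

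**The plan's own sample size reproduces and is not in dispute.** The t-test needs 94.11 per arm for a difference of 1.9 and SD 4. Multiplied by π/3 this is 98.55, so 99 per arm and 198 in total; 198 × 1.03 = 203.94, so 204.

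**Step 1: share with no SBM in Week 1.** The documents do not give it. Assume a negative binomial matched to mean m and SD s: k = m²/(s² − m), P0 = (k/(k + m))^k.

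- SC0232 placebo: k = 15.92/(7.29 − 3.99) = 4.82; P0 = (4.82/8.81)^4.82 = 0.0546, and × 102 = 5.6 subjects.
- SC0232 lubiprostone: k = 34.69/(16.16 − 5.89) = 3.38; P0 = (3.38/9.27)^3.38 = 0.0331, and × 102 = 3.4 subjects.

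**Step 2: simulate the main test with no effect on ratings.**

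- Trial: 204 subjects in 10 centers (8 of 20, 2 of 22), 1:1 within center.
- Test: van Elteren with weights 1/(n_h + 1) and tie-corrected variance; 10,000 trials per case.
- Assumed subject mean and SD: 1.8 and 0.9 for straining, 3.0 and 1.0 for consistency. Each SBM is rated around the subject mean with SD 0.6, rounded and clipped to the scale.
- A Week 1 with no SBM is scored 4 or 1.

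| Source | P0 placebo / lubiprostone | Subjects of 102 | Straining: two-sided (favouring lubiprostone) | Consistency: two-sided (favouring lubiprostone) |
|---|---|---|---|---|
| SC0131 | 0.0606 / 0.0555 | 6.2 / 5.7 | 4.8% (2.6%) | 4.7% (2.8%) |
| SC0232 | 0.0546 / 0.0331 | 5.6 / 3.4 | 5.4% (4.4%) | 5.7% (4.5%) |
| SC0831 | 0.0637 / 0.0117 | 6.5 / 1.2 | 9.3% (8.8%) | 9.4% (8.9%) |
| Design, SD 4 | 0.1575 / 0.0321 | 16.1 / 3.3 | 32% (32.1%) | 32% (32.4%) |

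Nominal values are 5% and 2.5%. Monte Carlo SE is about 0.2 points near 5% and 0.5 near 32%. The design row is an upper case only: its SD of 4 exceeds every placebo SD in Table 4.a (1.82 to 2.70). Repeats with 1,500 to 4,000 trials, one with a simpler rating model, gave 5.1% to 6.4% for straining at SC0232 rates and 9.1% to 10.3% at SC0831 rates.

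**Step 3: hand check of the shift.** The spurious straining difference is about (P0 placebo − P0 lubiprostone) × (4 − 1.8). For SC0232 this is 0.0215 × 2.2 = 0.047; for SC0831, 0.0520 × 2.2 = 0.114. The simulated shifts, in table order, are 0.01, 0.05, 0.11 and 0.27 points toward lubiprostone.

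**Step 4: would another planned analysis reveal it?** Robust ANOVA (bisquare M-estimation, 4,000 trials, same fill, straining) rejects in 5.2%, 6.0%, 9.3% and 38%, so it does not.

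**Step 5: the protocol's analysis without imputation.** With those subjects left out, the two-sided rate is 4.5% to 5.3% in all cases and the part favouring lubiprostone is 2.2% to 2.7%. Of the spurious straining benefits, 42%, 50%, 73% and 92% are no longer significant; the 42% for SC0131 is roughly what chance alone gives.

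**Step 6: ratings tied to frequency.** If subjects with fewer SBMs strain more (assumed correlation 0.3), the main-analysis straining rates are 5.3%, 5.3%, 7.0% and 21%.

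**The case against.** The strongest reply has five parts.

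- **The commitment still stands.** SAP 7.13 withdraws nothing, so the protocol's analysis remains due. True, but tables are programmed from the SAP, and an analysis absent from it is likely not to be produced.
- **Descriptive output shows part of the picture.** SAP 7.1 summarizes non-missing values. SAP 7.8 plans weekly histograms of SBM frequency and box plots of straining and consistency by arm, so the lowest Week 1 histogram bar would largely show the no-SBM subjects. This narrows the gap. It gives no test or interval and does not separate no SBM from no rating.
- **Counting a week with no SBM as failure is a legitimate composite.** Under that target, rejecting because placebo has more such weeks is correct, and the rates above are false positives only for an effect on the stools passed. This stands as a choice of target. Protocol 9.1.7.3 and SAP 7.8.2, however, define straining as an average over SBMs, so a composite should be named as one.
- **The realistic size is modest.** At SC0232 rates the arms differ by about 2 subjects of 102 and the two-sided rate barely moves; at SC0131 rates there is no inflation. These are secondary endpoints with no multiplicity adjustment. All of this stands.
- **Leaving subjects out conditions on a post-randomization event.** With correlation 0.3, the mean without imputation moves 0.004 to 0.054 points against lubiprostone and its two-sided error is 5.0% to 6.8%. Disagreement between the two analyses therefore does not prove that the assigned score drove the result. This is why the analysis is supportive only, as the protocol already labels it.

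**Conclusion.** The concern holds, and the SAP should be changed. The firm part is textual: the protocol promises an analysis without imputation, the SAP contains none, and the omission is not reported. It matters for straining and consistency because the 4/1 score lets a frequency effect enter a test of stool quality, and no other planned test or interval separates the two.

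The size is uncertain. On fits to Table 4.a it runs from no inflation (SC0131), through a directional tilt with little two-sided change (SC0232), to a two-sided rate of about 9% (SC0831). These figures rest on assumed negative binomial counts and assumed rating distributions, and they shrink if infrequent SBMs go with more straining. The 32% needs the design SD of 4, and the conclusion does not depend on it. The primary endpoint is not affected by the 4/1 rule.

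**What to change.** 1. Write the protocol 13.1.3 analysis without imputation into SAP 7.8.1 and 7.8.2 for the primary and secondary endpoints: the same stratified test, leaving out subjects with no observed value, with no LOCF, baseline or worst-score fill. Read any straining or consistency benefit alongside it.
2. Report the number imputed per arm and week, split into no SBM and SBM without a rating.
3. Add one sentence stating that the parameter-specific rules in 7.8.2 override the baseline rule in 7.8, and that only treatment-period values are carried forward, as in the protocol.
4. If the 4/1 score stays in the main analysis, describe the endpoint as counting a week with no SBM as failure.
5. Record these changes in SAP 7.13.

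The cost is SAP wording before unblinding and one extra set of tables. The main analysis and sample size do not change.

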9.1.7.5 Assessments of Abdominal Symptoms

The abdominal symptoms (bloating and discomfort upon waking in the morning) will be scored weekly on a 5-point scale, with a higher score indicating more severe symptoms. This will be assessed at Baseline and at Weeks 1, 2, 3, and 4. Subjects will be instructed to record weekly abdominal symptoms assessment in the diary. Diary entries will be reviewed at each Study Visit as per protocol schedule.

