6.0 DETERMINATION OF SAMPLE SIZE

Assuming equal allocation, a power of 90%, an alpha level of 0.05 for a 2-sided test, a placebo mean of 4, a treatment mean of 5.9 and a common standard deviation of 4 for SBM frequency at Week 1 and using the Wilcoxon-Mann-Whitney test [1], a total sample size of 198 is required. The Wilcoxon-Mann-Whitney test is a non-parametric test of the null hypothesis that the distribution is the same for both placebo and treatment responses against the alternative that there is a location difference between the two. The primary analysis will be conducted using the van Elteren test, which is a stratified version of the Wilcoxon-Mann-Whitney test; use of the Wilcoxon-Mann-Whitney test for sample size estimation will provide an approximate sample size for the van Elteren analysis. The estimates of placebo and treatment response are based on a previous study conducted by Sucampo Pharmaceuticals in the United States of America (Protocol No. SPI/0211SC0232).

The primary endpoint requires subjects to complete at least 4 days of the study diary, therefore assuming a non-evaluable rate of 3% by Day 4 an additional 6 subjects are required, giving a total of 204 subjects.

CROSS-REGIONAL TEMPLATE

Template Number:	C-TMPL-DO-801	Page:	9 of 28
Version Number:	1.2	Effective Date:	14 Sep 2015
This version replaces:	1.1		
Parent Document:	C-SOP-DO-800		
Template Title:	Statistical Analysis Plan (Legacy Takeda)		

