7.8 EFFICACY ANALYSIS

The primary and secondary endpoints will be derived from the daily diary data entered by patients.

Two-sided tests at a significance level of $\alpha=5\%$ will be used throughout unless otherwise stated. The null hypothesis is that lubiprostone is equal to placebo against the alternative that lubiprostone is different to placebo. All analyses will be performed using the FAS. Analyses specified for the PP are to be regarded as supportive evidence. There will be no adjustment for multiplicity.

All efficacy endpoints will be summarized by treatment and visit. If baseline measures are also defined and collected for an efficacy endpoint then change from Baseline at each visit will also be presented by summary statistics by treatment and visit. Change from baseline will be calculated as (post-baseline value) – (baseline value). Baseline is defined as the last recorded measurement prior to treatment.

For diary data, baseline values will be the average of all diary data from the screening period (Days -14 through -1, inclusive, relative to day of first dose). If more than 14 days of diary data are collected during the screening period only the data from Day -14 onwards will be used. If fewer than 8 days are available then the baseline value will be set to missing.

Centers may be pooled geographically if necessary for analysis purposes. This will be determined before database lock.

CROSS-REGIONAL TEMPLATE

Template Number: C-TMPL-DO-801

Page: 17 of 28

Version Number: 1.2

Effective Date: 14 Sep 2015

This version replaces: 1.1

Parent Document: C-SOP-DO-800

Template Title: Statistical Analysis Plan (Legacy Takeda)

For weekly SBM frequency, at least 4 days of diary data are required to compute a weekly estimate, if there are less than 4 days recorded in a week then the SBM frequency for that week will be set to missing.

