Abdominal Discomfort	0 = None: No abdominal discomfort 1 = Mild: Slight abdominal discomfort 2 = Moderate: Abdominal discomfort clearly felt 3 = Severe: Abdominal discomfort with pain 4 = Very severe: Abdominal discomfort with severe pain

The abdominal symptoms (bloating and discomfort) will be analyzed separately by van Elteren tests, stratified by center, at Weeks 1, 2, 3, and 4. A related 95% confidence interval and point estimate will be provided for the treatment difference; the confidence interval will be estimated by inverting the hypothesis test.

Additionally a cumulative logistic regression model will be used with treatment and center as factors as a sensitivity analysis. The estimated odds ratio and associated 95% CI will also be presented to aid interpretation of the clinical effect. The interaction between treatment and center will also be examined in a separate model.

If the assessment ratings are missing, then the LOCF method will impute the value from the value used for the most recent week. For Week 1 analysis where there is no value to carry forward then a value of 4 will be assumed. This assumption will be carried into later weeks if LOCF does not provide an estimate.

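### Four symptom scores have a baseline, but no planned test, estimate or confidence interval adjusts for it; adding it to the supportive models is a cheap improvement

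*SAP*

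**What the plan says.** **Baseline exists for all four scores.** For bloating and discomfort, Protocol 9.1.7.5 states: "This will be assessed at Baseline and at Weeks 1, 2, 3, and 4". Straining and stool consistency are entered in the diary for each bowel movement from Day -15 (Protocol Appendix E). SAP 7.8 defines the diary baseline as the average over the 14 days before first dose, missing if fewer than 8 days are available.

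**How it is used.** SAP 7.8 says that "change from Baseline at each visit will also be presented by summary statistics by treatment and visit", asks for box plots running from baseline to Week 4, and lets the baseline value stand in where a subject has no post-baseline efficacy data. For these four scores, 7.8.2 adds a fixed worst score at Week 1 when nothing can be carried forward.

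**How the scores are compared (SAP 7.8.2).**
- All four: van Elteren tests of the weekly values, stratified by center, with intervals obtained by inverting the test.
- Straining, and consistency by reference: "Additionally the endpoint will be analyzed using robust analysis of variance (ANOVA) models with center and treatment in the model as a sensitivity analysis".
- Bloating and discomfort: "Additionally a cumulative logistic regression model will be used with treatment and center as factors as a sensitivity analysis". The only further term mentioned is a treatment-by-center interaction.

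Protocol 13.1.3.2 has the same structure, with ordinary ANOVA. ANCOVA is in the SAP's abbreviation list, but no described analysis uses it.

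**The concern.** Protocol 6.2 selects these scores so that the evaluation goes beyond stool counts. They are severity ratings in a chronic condition. The entry criteria (Protocol 7.1 and 7.2) set no minimum for bloating or discomfort, so subjects can enter anywhere from 0 to 4, and a subject's starting level is likely to predict part of the later score.

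Two things follow when the starting level is left out. Stable differences between subjects stay in the error term, which lowers power. And if the arms differ at baseline by chance, part of that difference carries into every weekly comparison. The descriptive tables and plots would show such an imbalance, but no planned analysis would say whether the symptom difference survives correction for it.

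**Working it through.** **The plan's own figure.** SAP 6.0 assumes "a placebo mean of 4, a treatment mean of 5.9 and a common standard deviation of 4", 90% power and two-sided alpha 0.05, and concludes that "a total sample size of 198 is required".
- Normal approximation: n per arm = 2 x [4 x (1.960 + 1.282) / 1.9]^2 = 93.1. Times pi/3 for the Wilcoxon test this is 97.5, so 98 per arm and 196 in total.
- Noether's formula gives 203. The stated 198 lies between the two.
- 198 x 1.03 = 204.

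The figure reproduces, but it concerns Week 1 SBM frequency. The documents give no power or precision target for the four scores, and no rho. Rho is therefore assumed, from 0.2 to 0.7, with 102 subjects per arm.

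**Chance imbalance.** The standard error of a baseline difference is sqrt(2/102) = 0.140 SD, so 95% of trials fall within 1.96 x 0.140 = 0.27 SD. An imbalance of size d shifts the unadjusted weekly difference by rho x d (last column below). For scale, Protocol Table 4.a shows study SC0232 (118 and 119 subjects) with baseline SBM of 1.52 and 1.28, reported p = 0.012: 0.24 / sqrt((0.80^2 + 0.88^2)/2) = 0.29 SD. That is a different variable; it only shows what randomization at about this size can produce.

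**Difference scale.** Adjustment multiplies the residual variance by 1 - rho^2. If unadjusted power is 80%, adjusted power = Phi[(1.960 + 0.842)/sqrt(1 - rho^2) - 1.960].

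| Assumed rho | Variance factor | CI narrower by | Power 80% becomes | Shift from a 0.27 SD imbalance |
|---|---|---|---|---|
| 0.2 | 0.96 | 2.0% | 81.6% | 0.05 SD |
| 0.3 | 0.91 | 4.6% | 83.6% | 0.08 SD |
| 0.5 | 0.75 | 13.4% | 89.9% | 0.14 SD |
| 0.7 | 0.51 | 28.6% | 97.5% | 0.19 SD |

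**The planned model types, by simulation.** Settings: 204 subjects, 10 centers, a five-level score and a latent shift of 0.40 SD. Rho here is the latent correlation; the observed scores correlate slightly less (about 0.27, 0.45 and 0.63 at latent 0.3, 0.5 and 0.7). Power without and with baseline:

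| Model | rho 0.3 | rho 0.5 | rho 0.7 |
|---|---|---|---|
| Cumulative logit, 600 trials | 0.76 to 0.80 | 0.75 to 0.84 | 0.77 to 0.95 |
| Cumulative logit, separate 200 trials | 0.77 to 0.81 | 0.75 to 0.85 | 0.76 to 0.97 |
| Robust M-estimation, 600 trials | 0.76 to 0.78 | 0.74 to 0.83 | 0.77 to 0.94 |

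The gains are about 2-5 points at 0.3 (allowing for rounding), 9-10 at 0.5 and 17-21 at 0.7. The figure of 1-2 points at 0.2 comes from the formula (80% to 81.6%) and an ordinary linear model on five-level scores (75.3% to 76.8%, 3,000 trials). With 200 trials, the Monte Carlo standard error of one power figure is sqrt(0.75 x 0.25/200) = 0.03.

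**What happens to the odds ratio.** In the 200-trial cumulative logit runs, at rho 0.3, 0.5 and 0.7:
- Odds ratio: 0.50 to 0.48, 0.50 to 0.45, 0.49 to 0.36.
- Standard error of the log odds ratio: 0.263 to 0.265, 0.262 to 0.269, 0.263 to 0.280.

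Power rises because the estimate moves away from 1, not because its interval shrinks.

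**Validity of the planned tests.** With no treatment effect, the van Elteren test rejected in 5.4%, 5.0% and 4.7% of 3,000 simulated trials at latent rho 0.3, 0.5 and 0.7.

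**The case against.** The strongest reply is that nothing here is an error. Randomization protects the van Elteren tests, the endpoints are secondary with no power target, and leaving out baseline is a choice among valid methods. That stands. A reader might infer that the planned comparisons are biased or invalid, but the documents do not support this, and simulated type I error is about 5%.

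Four other stronger readings also fail:
- *That the fix strengthens the main tests.* The covariate goes only into models that the SAP calls sensitivity analyses. The van Elteren p-values and their test-inverted intervals do not change.
- *That imbalance passes through in full.* It passes in proportion to rho, and SAP 7.8 would make it visible in the change summaries and box plots, though not correct it.
- *That the odds ratio becomes more precise.* It does not. It becomes a different, conditional quantity, and at rho 0.7 the change is substantial.
- *That all four scores lose equally.* Inclusion criteria 4 and 5 (Protocol 7.1) partly restrict straining and consistency at entry. Earlier trials averaged 1.28 to 1.68 SBMs per week at baseline (Table 4.a), or about 2.6 to 3.4 rated movements in two weeks, so those baselines are noisy. If SBM counts were Poisson (an assumption), exp(-2 x 1.68) = 3% to exp(-2 x 1.28) = 8% of subjects would have no SBM to rate. The simulations include neither this nor the worst-score imputation, and both may lower rho.

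**Conclusion.** The point holds as a cheap improvement. All four scores have a baseline, and no planned test, estimate or confidence interval for them adjusts for it. The cost is lower power in the supportive models and no analysis that corrects a chance imbalance. An imbalance at the 95% limit (0.27 SD) would move a weekly difference by about 0.08 to 0.19 SD for rho between 0.3 and 0.7.

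The size rests wholly on assumed values of rho. At 0.2 the power gain is negligible; at 0.5 or above it is worth having. Bloating and discomfort, with no entry threshold, have the better case, and straining and consistency may be at the low end. For the robust ANOVA the gain includes a more precise estimate of the same difference. For the cumulative logit it is power and correction of imbalance only.

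**What to change.** In SAP 7.8.2, before unblinding:
- Add the subject's baseline score as a covariate to the cumulative logistic models for bloating and discomfort, and to the robust ANOVA models for straining and consistency.
- For subjects without a baseline (no SBM in screening, or fewer than 8 diary days), set the covariate to a fixed value and include a missing-baseline indicator, so that no randomized subject drops out of the model.
- Report the adjusted odds ratio or difference with its 95% CI beside the planned unadjusted result.
- Keep the van Elteren tests as the main tests, unchanged.
- Label the adjusted odds ratio as conditional on baseline. State that it is expected to lie further from 1 than the unadjusted one, substantially so at high rho, and that its interval on the log scale is not expected to be narrower.

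The cost is one covariate and one indicator in models already planned, using data already collected. The downside is a second odds ratio with a different meaning, which the report must explain.

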As the primary endpoint is within the first week of study treatment and only 4 days of diary collection are required it is not anticipated that missing values should be a cause of concern therefore the LOCF technique will be used to impute missing values for efficacy analysis purposes only. For a given subject, the most recent nonmissing data point will be carried forward to the subsequent week where data are missing. Details for each efficacy parameter are given below. It is expected, based on previous studies, that the number of subjects with in-sufficient post baseline data for the primary endpoint will be small therefore a simple approach to handling missing data will be used. Where there is no post baseline efficacy data then the baseline value will be used, it is expected that the number of SBMs should increase for those on treatment, therefore using a baseline value for missing post baseline data assumes no treatment effect, this approach can be considered conservative,. To examine the effect of the requirement to have at least a minimum of 4 days post baseline efficacy data for the primary endpoint an additional analysis, stratified by center, of the primary endpoint, using the stratified van Elteren test [2], will be conducted using all valid SBM data post baseline even when less than 4 days data is present, only where there is no post baseline data will baseline be used in this analysis.

An SBM is defined as any BM that does not occur within 24 hours after rescue medication use. Certain periods after taking rescue medication will be defined as “blackout periods” during which BMs are considered as non-spontaneous. Blackout periods, including those with missing or partial times for rescue medication use in the diary, will be handled as follows:

0-24 hours post rescue medication intake if the time is fully specified.

0-24 hours post rescue medication intake if the hour is present, but the minute is missing. The blackout time will commence from the imputed time. If the minutes are incomplete or missing from either the rescue medication or bowel movement entry then it is assumed that the missing values are zero and an imputed time will be calculated. e.g.

1	5			=	1	5	0	0
2	1	5		=	2	1	5	0

0-48 hours, beginning from midnight on the day the rescue medication intake is recorded for, if the hour is missing from the time entry for the rescue medication.

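### A missing Week 1 bloating or discomfort rating is scored as very severe in the main analysis, which does not fit the SAP's own baseline rule or the protocol's supportive-only worst case, and is not reliably conservative

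*SAP*

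**What the plan says.** Bloating and discomfort are each rated 0 to 4, once a week, "every 7 days on the last day of each treatment week upon waking in the morning" (SAP 7.8.2). The top categories read "4 = Very severe: Extremely strong abdominal distension" and "4 = Very severe: Abdominal discomfort with severe pain". The main test is stated as follows: "The abdominal symptoms (bloating and discomfort) will be analyzed separately by van Elteren tests, stratified by center, at Weeks 1, 2, 3, and 4". A cumulative logistic model is the sensitivity analysis.

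For missing ratings, SAP 7.8.2 carries forward the value from the most recent week. It then adds: "For Week 1 analysis where there is no value to carry forward then a value of 4 will be assumed". The next sentence reads: "This assumption will be carried into later weeks if LOCF does not provide an estimate".

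Two other places bear on the same gap:

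- SAP 7.8, in the general efficacy rules: "Where there is no post baseline efficacy data then the baseline value will be used". The SAP calls this conservative because it assumes no treatment effect.
- Protocol 13.1.3 makes LOCF of treatment-period data the main rule. It adds supportive analyses, one without imputation and one in which "missing values are assigned the worst case values recorded in the study by any subject for that endpoint at that time".

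For the primary endpoint, SAP 7.8.1 uses worst-case values only in a sensitivity analysis. Protocol 9.1.7.5 has the abdominal symptoms rated at baseline as well as at Weeks 1 to 4.

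**The concern.** The rating is a single entry on the last morning of the week, whereas the primary endpoint needs only 4 diary days. A subject who withdraws after Day 4 but before that morning, or who misses that one entry, can be evaluable for SBM frequency and still have no Week 1 symptom score. The SAP's reassurance that little will be missing is argued for the primary endpoint and does not carry over. The FAS also includes randomized subjects who were never treated. With no ratings, they would score 4 on both symptoms at all four weeks.

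On the natural reading, such a subject is scored very severe even if the screening diary recorded no bloating. The comparison then partly measures who missed an entry or withdrew. Discontinuation for adverse events, or for rescue use within 48 hours of the first dose, could differ by arm, so equal missingness cannot be assumed. A worst score looks cautious, but it is cautious about lubiprostone only when more lubiprostone ratings are missing. When more placebo ratings are missing, it favors lubiprostone.

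**Working it through.** **Figures in the plan.** The documents give no figure for this endpoint and no expected number of missing ratings. The only related figures belong to the primary endpoint. The 198 evaluable subjects reproduce: Wilcoxon-Mann-Whitney power under a normal shift with means 4 and 5.9 and SD 4 is 0.902 at 99 per arm. The 204 follows as 198 x 1.03 = 203.9. These fix the trial size used below (102 per arm). The 3% non-evaluable rate by Day 4 (SAP 6.0) is the nearest documented guide to missingness.

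**Assumed, not in the documents.** Placebo Week 1 scores 0 to 4 have probabilities 10/25/35/22/8%. The cumulative odds ratio for lubiprostone is 2. Baseline has the same distribution as placebo. There are 10 equal centers (the protocol plans about 10). Missingness is unrelated to the score.

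**Mean difference.**

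- Placebo mean: 0.25 + 0.70 + 0.66 + 0.32 = 1.93.
- Doubling the cumulative odds turns 0.10/0.35/0.70/0.92 into 0.1818/0.5185/0.8235/0.9583. The lubiprostone mean is the sum of the complements: 0.8182 + 0.4815 + 0.1765 + 0.0417 = 1.518.
- True difference: 1.518 - 1.93 = -0.412.

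Let a and b be the proportions missing on lubiprostone and placebo.

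- Imputing 4 shifts the difference by a(4 - 1.518) - b(4 - 1.93) = 2.482a - 2.07b.
- Imputing baseline shifts it by a(1.93 - 1.518) = 0.412a.

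For 8%/3%, imputing 4 gives -0.412 + 0.199 - 0.062 = -0.28, and baseline gives -0.412 + 0.033 = -0.38. For 3%/8%, imputing 4 gives -0.412 + 0.074 - 0.166 = -0.50.

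**Power and false rejection** (simulated van Elteren test, two-sided 5%):

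| Missing, lubiprostone/placebo | Difference, value 4 | Difference, baseline | Power, value 4 | Power, baseline | Rejection with no effect, value 4 |
|---|---|---|---|---|---|
| 3%/3% | -0.40 | -0.40 | 71% | 74% | 5% |
| 4%/2% | -0.35 | -0.40 | 63% | 74% | 6% |
| 8%/3% | -0.28 | -0.38 | 45% | 70% | 9% |
| 3%/8% | -0.50 | -0.40 | 85% | not tabulated | 9%, by symmetry |

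Repeat simulations agree within about 3 points. With 1,500 trials the standard error at 70% is sqrt(0.7 x 0.3/1500), or 1.2 points, so the gap at 3%/3% is small even against simulation error.

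**Second set of assumptions, no true effect.** On-treatment probabilities are 15/30/35/15/5% (mean 1.65) and baseline probabilities 5/20/40/25/10% (mean 2.15). With six placebo ratings missing and none on lubiprostone (6/204 = 3% overall), imputing 4 shifts the difference by -(6/102)(4 - 1.65) = -0.14. Baseline shifts it by -(6/102)(2.15 - 1.65) = -0.03. False significance in favor of lubiprostone (nominal 2.5%) is 9.8% with value 4, 4.0% with baseline and 2.4% with observed cases. With ten placebo and two lubiprostone ratings missing, the figures are 12.8%, 3.8% and 2.4%. Six missing on lubiprostone and none on placebo mirrors the bias: 10.3% false significance for placebo with value 4.

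**The case against.** Several points on the other side have weight.

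- **The wording may allow baseline to be carried.** The value 4 applies only where nothing can be carried forward. SAP 7.8 speaks of the most recent nonmissing data point and drops the protocol's limit to treatment-period data. If baseline could never be carried, that condition would be redundant at Week 1. A reader might infer that the SAP certainly discards the screening rating; the text does not settle that. The contrary reading is still the more natural one. Under the protocol's LOCF nothing exists to carry at Week 1, and the parallel stool-consistency sentence sets the clause off with commas, as an explanation.
- **The protocol has no rule for this gap.** Its LOCF fills only a subsequent week, and it leaves detail to the SAP. A reader might infer that the SAP breaks an explicit Week 1 rule; it does not. What stands is that the protocol gives worst-case values supportive status and the SAP puts one in the main analysis.
- **Parameter-specific rules follow the general one.** SAP 7.8 says so, which suggests that 4 is deliberate. The baseline rule is nevertheless worded for efficacy data in general; only its justification mentions SBMs. A subject with no post-baseline ratings therefore falls under both rules.
- **There are safeguards.** The protocol promises an analysis without imputation, diaries are reviewed at Day 8, and phone reminders and dated clarifications are allowed. These reduce the risk, but SAP 7.8.2 does not list the no-imputation analysis for this endpoint.
- **Few ratings may be missing.** Near 3% in both arms the harm is negligible. This stands, and it limits the size of the point.

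**Conclusion.** The point holds as a conflict to reconcile and a poor choice of main-analysis rule for a secondary endpoint. The primary result is unaffected.

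The direction of the bias needs no distributional assumption beyond imperfect symptom control: imputing the maximum raises the mean of the arm with more missing ratings. Its size rests on the assumed distributions and missing rates. It runs from almost nothing (3%/3%), through a power loss of 11 points (4%/2%: 63% against 74%), to a loss of 25 points and 9% rejection under no effect (8%/3%).

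A reader might take the 8%/3% case as what to expect. The documents do not support that: they give only a 3% non-evaluable rate, for another endpoint and not by arm. A reader might also infer that the rule always works against lubiprostone, or always for it. It does neither, which is why it cannot be defended as conservative. The protocol's supportive worst-case analysis offers little contrast at Week 1, because a fixed 4 equals the worst recorded value whenever any subject records a 4.

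**What to change.** In SAP 7.8.2, Weekly Abdominal Symptoms Score:

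1. State that a missing Week 1 rating takes the subject's own baseline score for that symptom, defined as the last screening rating. Say that this is an exception to SAP 7.8, which averages diary data over Days -14 to -1 and sets baseline to missing with fewer than 8 days. A single rating stays an ordinal category for the cumulative logistic model; an average may not.
2. Use 4 only if the baseline rating is also missing, or in a named worst-case sensitivity analysis for this endpoint. The SAP currently specifies a worst-case analysis only for SBM frequency.
3. List the analysis without imputation that protocol 13.1.3 promises.
4. Say explicitly whether LOCF may use screening data, so that SAP 7.8, SAP 7.8.2 and the protocol agree.
5. Review the same device for straining (4) and stool consistency (1) in the same section, so that the secondary endpoints are handled consistently.

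The cost is SAP wording and some programming before unblinding. No new data are needed, because the baseline rating is already collected.
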